#### **6.1.1.2 Patient Entry Procedure**

---

†A female of childbearing potential is a sexually mature woman who: 1) has not undergone a hysterectomy or bilateral oophorectomy; or 2) has not been naturally postmenopausal for at least 24 consecutive months (i.e., has had menses at any time in the preceding 24 consecutive months).

- Once an eligible candidate has been identified for the study, the Research Study Specialist should be called to bring the IRB approved informed consent form and HIPAA Authorization to the Investigator and potential participant.
- The Investigator will consent the participant and verify the eligibility criteria of the candidate. No study related procedures will be performed prior to the participant signing the consent form.
- Anticoagulated bone marrow and peripheral blood specimens and bone marrow biopsies will be placed on ice and sent to [name] lab for gene expression assays required for this study.

### **6.1.1.3**

The starting dose of REVLIMID® will be 10 mg days 1-28 with the first dose reduction going to 5 mg days 1-28 of a 28 day cycle. Therapy will cease if there is no response after 12 weeks. Patients responding to treatment will continue on Revlimid® until disease progression or unmanageable toxicities.

- Based on previous trials in del 5q MDS patient one hundred percent of patients reported at least one adverse event; 89% (131/148) experienced at least one grade 3/4 adverse event. Eighty percent required a dose delay and/or reduction for toxicity during the study. Thirty-four percent required a second dose delay/reduction. Dose adjustment recommendations for neutropenia and thrombocytopenia are provided in product labeling. Patients should have complete blood counts monitored weekly for the initial 12 weeks and at least monthly thereafter. Thromboembolic events were rare in the Revlimid® studies in MDS patients with deletion 5q cytogenetic abnormalities. However, in recently reported trials conducted in multiple myeloma, a significantly increased risk of deep venous thrombosis and pulmonary embolism was observed in patients treated with Revlimid® combination therapy. An elevated risk of thrombosis has also been reported when erythropoietin is used during Revlimid® treatment. The role of prophylactic anticoagulation and/or antiplatelet therapy with Revlimid® has not been adequately assessed. Any prophylactic measures should be prescribed after a careful assessment of individual risk factors.
- Patients with serum creatinine above 2.5 mg/dl were excluded from the studies. Because Revlimid® is predominately excreted by the kidney, renal function should be carefully monitored.
- Females should be advised to avoid pregnancy while taking Revlimid®. Revlimid is an analogue of thalidomide, a known human teratogen that causes severe human birth defects. Additional

reproductive toxicity studies will be performed to assess any potential Revlimid® teratogenicity. Only prescribers and pharmacists registered under the RevAssist® program can prescribe or dispense Revlimid®. Patients must agree to comply with the RevAssist® program requirements.

[figure not shown]
- Clinical toxicity has been infrequent with administration of REVCLIMID® (see section 4.9). Cases of neutropenia and thrombocytopenia have been reported in the phase I/II experience in the majority of patients and appear to be dose and/or duration dependent. MDS patients with existing neutropenia and/or thrombocytopenia should be monitored closely during treatment for potential exacerbation that may merit a treatment hiatus and dose reduction as described below.

## **6.1.2 Study Drug**

### **6.1.2.1 Lenalidomide Description**

REVCLIMID® (lenalidomide), a thalidomide analogue, is an immunomodulatory agent with anti-angiogenic properties. The chemical name is 3-(4-amino-1-oxo 1,3-dihydro -2H-isoindol-2-yl) piperidine-2,6-dione and it has the following chemical structure:

*Chemical Structure of Lenalidomide*

3-(4-amino-1-oxo 1,3-dihydro-2H-isoindol-2-yl) piperidine-2,6-dione

The empirical formula for lenalidomide is C13H13N3O3, and the gram molecular weight is 259.3.

Lenalidomide is an off-white to pale-yellow solid powder. It is soluble in organic solvent/water mixtures, and buffered aqueous solvents. Lenalidomide is more soluble in organic solvents and low pH solutions. Solubility was significantly lower in less acidic buffers, ranging from about 0.4 to 0.5 mg/ml. Lenalidomide has an asymmetric carbon atom and can exist as the optically active forms S(-) and R(+), and is produced as a racemic mixture with a net optical rotation of zero.

### **6.1.2.2 CLINICAL PHARMACOLOGY**

#### **Mechanism of Action:**

The mechanism of action of lenalidomide remains to be fully characterized. Lenalidomide possesses immunomodulatory and antiangiogenic properties. Lenalidomide inhibited the secretion of pro-inflammatory cytokines and increased

the secretion of anti-inflammatory cytokines from peripheral blood mononuclear cells. Lenalidomide inhibited cell proliferation with varying effectiveness (IC50s) in some but not all cell lines. Of cell lines tested, lenalidomide was effective in inhibiting growth of Namalwa cells (a human B cell lymphoma cell line with a deletion of one chromosome 5) but was much less effective in inhibiting growth of KG-1 cells (human myeloblastic cell line, also with a deletion of one chromosome 5) and other cell lines without chromosome 5 deletions. Lenalidomide inhibited the expression of cyclooxygenase-2 (COX-2) but not COX-1 in vitro.

#### **6.1.2.3 Pharmacokinetics and Drug Metabolism:**

##### **Absorption:**

Lenalidomide, in healthy volunteers, is rapidly absorbed following oral administration with maximum plasma concentrations occurring between 0.625 and 1.5 hours post-dose. Co-administration with food does not alter the extent of absorption (AUC) but does reduce the maximal plasma concentration (Cmax) by 36%. The pharmacokinetic disposition of lenalidomide is linear. Cmax and AUC increase proportionately with increases in dose. Multiple dosing at the recommended dose-regimen does not result in drug accumulation.

Pharmacokinetic sampling in myelodysplastic syndrome (MDS) patients was not performed. In multiple myeloma patients maximum plasma concentrations occurred between 0.5 and 4.0 hours post-dose both on Days 1 and 28. AUC and Cmax values increase proportionally with dose following single and multiple doses. Exposure (AUC) in multiple myeloma patients is 57% higher than in healthy male volunteers.

##### **Pharmacokinetic Parameters:**

##### **Distribution:**

In vitro (C)-lenalidomide binding to plasma proteins is approximately 30%.

##### **Metabolism and Excretion:**

The metabolic profile of lenalidomide in humans has not been studied. In healthy volunteers, approximately two-thirds of lenalidomide is eliminated unchanged through urinary excretion. The process exceeds the glomerular filtration rate and therefore is partially or entirely active. Half-life of elimination is approximately 3 hours.

#### **6.1.2.4 Supplier(s)**

Celgene Corporation will supply Revlimid® (lenalidomide) to study participants at no charge through the RevAssist® program. All physicians who prescribe lenalidomide for research subjects enrolled into this trial and all research subjects enrolled into this trial must be registered in and must comply with all requirements of the RevAssist® program.

#### **6.1.2.5 Dosage form**

Lenalidomide will be supplied as capsules for oral administration.

#### **6.1.2.6 Packaging**

Lenalidomide will be shipped directly to patients. Bottles will contain a sufficient number of capsules for one cycle of dosing.

#### **6.1.2.7 Storage**

Lenalidomide should be stored at room temperature away from direct sunlight and protected from excessive heat and cold.

#### **6.1.2.8 Prescribing Information**

Lenalidomide (Revlimid®) will be provided to research subjects for the duration of their participation in this trial at no charge to them or their insurance providers.

Lenalidomide will be provided in accordance with the RevAssist® program. Per standard RevAssist® requirements all physicians who prescribe lenalidomide for research subjects enrolled into this trial, and all research subjects enrolled into this trial, must be registered in and must comply with all requirements of the RevAssist® program. Prescriptions must be filled within 7 days. **Only enough lenalidomide for one cycle of therapy will be supplied to the patient each cycle.**

## **6.2 Screening and Eligibility**

The Investigator is responsible for keeping a record of all subjects who sign an Informed Consent Form for entry into the study. All subjects will be screened for eligibility. Screening procedures are outlined in Section 2, Schedule of Study Assessments and unless otherwise specified, must take place within 28 days prior to initiation of therapy.

Approximately 56 of subjects with transfusion-dependent, **non-del(5q)** low/Intermediate-1 risk Myelodysplastic Syndrome will be screened for enrollment and must meet the eligibility criteria below.

### **6.2.1 Inclusion Criteria**

Subjects must meet the following inclusion/exclusion criteria to be eligible for the study.

#### **Inclusion criteria**

1. Understand and voluntarily sign an informed consent form.

2. Age  $\geq$  21 years at the time of signing the informed consent form.
  3. Able to adhere to the study visit schedule and other protocol requirements.
  4. A confirmed diagnosis (using standard FAB criteria) of a myelodysplastic syndrome with low/Int-1 risk and with a non-del(5q) karyotype must be established.
  5. Patients must have transfusion dependence (at least 2 units within 8 weeks prior to starting therapy).
  6. All transfusion dependent **non**-del(5q) low/Int-1 risk patients will be eligible for treatment with Revlimid®
  7. Newly diagnosed as well as previously treated patients will be eligible
  8. Patients with primary de novo or secondary MDS will be eligible
  9. All previous cancer therapy, including radiation, hormonal therapy and surgery, must have been discontinued at least 4 weeks prior to treatment in this study.
10. ECOG performance status of 0-2 at study entry (see Appendix II).
11. Laboratory test results within these ranges:
- Absolute neutrophil count  $> 250/\mu\text{L}$
  - Platelet count  $> 30,000/\mu\text{L}$
  - Serum creatinine  $\leq 2.0 \text{ mg/dL}$
  - Total bilirubin  $\leq 1.5 \text{ mg/dL}$
  - AST (SGOT) and ALT (SGPT)  $\leq 3 \times \text{ULN}$
  - BUN  $\leq 2 \times \text{ULN}$
12. Disease free of prior malignancies for  $\geq 2$  years with exception of currently treated basal cell, squamous cell carcinoma of the skin, or carcinoma "in situ" of the cervix or breast.
13. All study participants must be registered into the mandatory RevAssist® program, and be willing and able to comply with the requirements of RevAssist®.

14. Females of childbearing potential (FCBP)† must have a negative serum or urine pregnancy test with a sensitivity of at least 50 mIU/mL within 10 – 14 days prior to and again within 24 hours of prescribing lenalidomide (prescriptions must be filled within 7 days) and must either commit to continued abstinence from heterosexual intercourse or begin TWO acceptable methods of birth control, one highly effective method and one additional effective method AT THE SAME TIME, at least 28 days before she starts taking lenalidomide. FCBP must also agree to ongoing pregnancy testing. Men must agree to use a latex condom during sexual contact with a FCBP even if they have had a successful vasectomy. See Appendix I: Risks of Fetal Exposure, Pregnancy Testing Guidelines and Acceptable Birth Control Methods.

### **6.2.2 Exclusion criteria**

1. Any serious medical condition, laboratory abnormality, or psychiatric illness that would prevent the subject from signing the informed consent form.
2. Pregnant or breast feeding females. (Lactating females must agree not to breast feed while taking lenalidomide).
3. Any condition, including the presence of laboratory abnormalities, which places the subject at unacceptable risk if he/she were to participate in the study or confounds the ability to interpret data from the study.
4. Any clinically significant cardiac disease, including congestive heart failure
5. Liver function studies including SGOT/SGPT > 3 x ULN
6. Clinically significant renal disease.
7. Any previous chemotherapy, hematopoietic growth factors, erythropoietin, or cytokines within 4 weeks of starting treatment. Note: prior therapy with G-CSF within 4 weeks is allowed.
8. Use of any other experimental drug or therapy within 28 days of baseline.
9. Known hypersensitivity to thalidomide.
10. The development of erythema nodosum if characterized by a desquamating rash while taking thalidomide or similar drugs.

---

† A female of childbearing potential is a sexually mature woman who: 1) has not undergone a hysterectomy or bilateral oophorectomy; or 2) has not been naturally postmenopausal for at least 24 consecutive months (i.e., has had menses at any time in the preceding 24 consecutive months).

11. Any prior use of lenalidomide. (Patients with prior therapy with thalidomide will be eligible as long as at least 4 weeks have elapsed between end of the drug and accrual on the present trial)
12. Concurrent use of other anti-cancer agents or treatments.
13. Known positive for HIV or infectious hepatitis, type B or C.
14. Life expectancy < 3 months

### **6.3 Visit schedule and assessments**

Screening Assessments and all on study scheduled visits and assessments are outlined in Section 2 Table of Study Assessments, and Section 6.1.1.

At treatment discontinuation, subjects will undergo off study evaluations per the Schedule of Assessments, Section 2. In addition, a safety assessment will be done approximately 30 days ( $\pm 7$  days) post the last dose of study drug.

### **6.4 Drug Administration**

#### **6.4.1 Treatment assignments**

Transfusion-dependent, **non-del(5q)** low/intermediate-1 risk myelodysplastic syndrome patients will be eligible for this study.

#### **6.4.2 Dosing regimen**

The planned dose of lenalidomide for investigation is 10 mg/day, orally on days 1-28 for a 28 day cycle. Dosing will be in the morning at approximately the same time each day. Prescriptions must be filled within 7 days.

If a dose of lenalidomide is missed, it should be taken as soon as possible on the same day. If it is missed for the entire day, it should not be made up.

Patients who take more than the prescribed dose of lenalidomide should be instructed to seek emergency medical care if needed and contact study staff immediately.

Subjects experiencing adverse events may need study treatment modifications (See section 6.5).

#### **6.4.3 Special Handling Instructions**

Females of childbearing potential should not handle or administer lenalidomide unless they are wearing gloves.

#### 6.4.4 Record of administration

Accurate records will be kept of all study drug administration (including prescribing and dosing) will be made in the source documents.

### 6.5 Dose Continuation, Modification and *Interruption*

Patients will be evaluated for adverse events at each visit with the National Cancer Institute (NCI) Common Toxicity Criteria (CTC) used as a guide to the grading of severity (See Appendix III). Dosing should be modified per the dose reduction steps in Section 6.5.1 for toxicities as outlined Section 6.5.2 and in the dose modification table in Section 6.5.3 (Table 2).

#### 6.5.1 Dose Reduction Steps

**Table 1: LENALIDOMIDE Dose Reduction Steps**

Starting Dose	10 mg daily on Days 1-28 every 28 days
Dose Level – 1	5 mg daily on Days 1-28 every 28 days
Dose Level – 2	5 mg every other day on Days 1-28 every 28 days
Dose Level – 3	5 mg q 3 days on Days 1-28 every 28 days

#### 6.5.2 Instructions for initiation of a New Cycle

A new course of treatment may begin on the scheduled Day 1 of a new cycle if:

- The ANC is  $\geq 250/\mu\text{l}$  or at least half of baseline
- The platelet count is  $\geq 30,000/\mu\text{l}$  or at least half of baseline
- Any drug-related rash or neuropathy that may have occurred has resolved to  $\leq$  grade 1 severity;
- Any other drug-related adverse events that may have occurred have resolved to  $\leq$  grade 2 severity.

If these conditions are not met on Day 1 of a new cycle, the subject will be evaluated weekly and a new cycle of treatment will not be initiated until the toxicity has resolved as described above. Resolution of the toxicity must occur within 4 weeks or the patient will be removed from study. If lenalidomide dosing was halted during the previous cycle and was restarted with a one-level dose reduction without requiring an interruption for the remainder of the cycle, then that reduced dose level will be initiated on Day 1 of the new cycle. **If lenalidomide dosing was omitted for the remainder of the previous cycle or if the new cycle is delayed due to toxicity newly encountered on the**

**scheduled Day 1**, then the new cycle will be started with a one-level dose reduction of lenalidomide.

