### 6.5.3 Instructions for dose modifications or interruption during a cycle.

Table 2: Dose Modifications	
NCI CTC Toxicity Grade (unless otherwise noted)	Dose Modification Instructions
If baseline ANC ≥ 1000/ mm^3: Grade 3 neutropenia associated with fever (temperature ≥ 38.5° C) or Grade 4 neutropenia	
 
Hold (interrupt) lenalidomide dose.
 
Follow CBC weekly.
 
If neutropenia has resolved to ≤ grade 2 prior to Day 21, restart lenalidomide at next lower dose level and continue through the scheduled end of the cycle. Otherwise, omit for remainder of cycle and reduce the dose of lenalidomide by 1 dose level at the start of the next cycle. Omitted doses are not made up. If neutropenia is the only toxicity for which a dose reduction is required, G-CSF may be used and the lenalidomide dose maintained
 

If baseline ANC ≤ 1000/ mm^3: Grade 3 neutropenia associated with fever (temperature ≥ 38.5° C) or ANC < 50% of baseline	
 
Hold (interrupt) lenalidomide dose.
 
Follow CBC weekly.
 
If ANC has recovered to ≥50% of baseline and fever has resolved prior to Day 21, restart lenalidomide at next lower dose level and continue through the scheduled end of the cycle. Otherwise, omit for remainder of cycle and reduce the dose of lenalidomide by 1 dose level at the start of the next cycle. Omitted doses are not made up. If neutropenia is the only toxicity for which a dose reduction is required, G-CSF may be used and the lenalidomide dose maintained
 

If baseline platelet count ≥ 50,000/mm^3: Thrombocytopenia ≥Grade 3 (platelet count < 50,000/mm^3)	
 
Hold (interrupt) lenalidomide dose.
 
Follow CBC weekly.
 
If thrombocytopenia has recovered to ≤ grade 2 prior to Day 21, restart lenalidomide at next lower dose level and continue through the scheduled end of the cycle. Otherwise, omit for remainder of cycle and reduce the dose of lenalidomide by 1 dose level at the start of the next cycle. Omitted doses are not made up.
 

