If baseline platelet count < 50,000/mm^3: Platelet count < 50% of baseline	
 
Hold (interrupt) lenalidomide dose.
 
Follow CBC weekly.
 
If platelet count resolves to ≥50% of baseline prior to Day 21, restart lenalidomide at next lower dose level and continue through the scheduled end of the cycle. Otherwise, omit for remainder of cycle and reduce the dose of lenalidomide by 1 dose level at the start of the next cycle. Omitted doses are not made up.
 

Table 2: Dose Modifications	
NCI CTC Toxicity Grade (unless otherwise noted)	Dose Modification Instructions
Non-blistering rash	
 
• If Grade 3, hold (interrupt) lenalidomide dose. Follow weekly.
 
• If the toxicity resolves to ≤ grade 1 prior to Day 21, restart lenalidomide at next lower dose level and continue through the scheduled end of the cycle. Otherwise, omit for remainder of cycle and reduce the dose of lenalidomide by 1 dose level at the start of the next cycle. Omitted doses are not made up.
 

Grade 4	
 
• If Grade 4, discontinue lenalidomide. Remove patient from study.
 

Desquamating (blistering) rash- any Grade	
 
• Discontinue lenalidomide. Remove patient from study.
 

Neuropathy	
 
• If Grade 3, hold (interrupt) lenalidomide dose. Follow at least weekly.
 
• If the toxicity resolves to ≤ grade 1 prior to Day 21, restart lenalidomide at next lower dose level and continue through the scheduled end of the cycle. Otherwise, omit for remainder of cycle and reduce the dose of lenalidomide by 1 dose level at the start of the next cycle. Omitted doses are not made up.
 

Grade 4	
 
• If Grade 4, discontinue lenalidomide. Remove patient from study.
 

Venous thrombosis/embolism ≥ Grade 3	
 
• Hold (interrupt) lenalidomide and start anticoagulation; restart lenalidomide at investigator's discretion (maintain dose level).
 
• Omit lenalidomide for remainder of cycle. See Anticoagulation Consideration (Section 6.6.1.2)
 

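### The count rules for starting a new cycle (Section 6.5.2) overlap with the hold rules in Table 2 (Section 6.5.3), and the protocol does not say which prevails.

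*Combined protocol and SAP*

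**What the plan says.** Section 6.5 directs that dosing follow both Section 6.5.2 and Table 2 in Section 6.5.3. It gives no order of precedence.

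Section 6.5.2 lists four conditions for Day 1 of a new cycle, introduced by "A new course of treatment may begin on the scheduled Day 1 of a new cycle if". The two count conditions are "The ANC is $\geq 250/\mu\text{l}$ or at least half of baseline" and "The platelet count is $\geq 30,000/\mu\text{l}$ or at least half of baseline". The third concerns rash and neuropathy. The fourth begins "Any other drug-related adverse events that may have occurred have resolved to" and sets the limit at grade 2 or lower. If the conditions are not met, the patient is checked weekly for up to 4 weeks. A cycle that follows an omitted remainder of a cycle, or that is delayed for new toxicity on Day 1, starts one dose level lower.

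Table 2, headed as applying during a cycle, orders the drug to be held:

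- Baseline platelets of 50,000 or more: the trigger is "Thrombocytopenia ≥Grade 3 (platelet count < 50,000/mm" (per cubic millimetre, the same unit as per µl). Restart needs recovery: "If thrombocytopenia has recovered to ≤ grade 2 prior to Day 21, restart lenalidomide at next lower dose level".
- Baseline platelets below 50,000: the trigger is "Platelet count < 50% of baseline".
- Baseline ANC of 1000 or less: the trigger is ANC below half of baseline, or febrile grade 3 neutropenia. The restart condition is "If ANC has recovered to ≥50% of baseline and fever has resolved prior to Day 21".
- Baseline ANC of 1000 or more: the trigger is grade 4 neutropenia, or febrile grade 3. No count is given for grade 4.

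**The concern.** One Day 1 count can satisfy the condition to start and the condition to hold. With baseline platelets of 120,000 and a Day 1 count of 35,000, Section 6.5.2 permits a start because 35,000 exceeds 30,000, while Table 2 says hold because it is below 50,000. With baseline ANC of 900 and a Day 1 ANC of 300, Section 6.5.2 permits a start because 300 exceeds 250, while Table 2 says hold because 300 is below 450. Both baselines meet the entry criteria (platelets above 30,000, ANC above 250).

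These are the rules for the toxicity the protocol itself expects. Section 6.1.1.3 reports neutropenia and thrombocytopenia in the majority of phase I/II patients and points forward to the hold and reduction rules.

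The reading chosen also changes exposure. A start under Section 6.5.2 can keep the current dose level. A Table 2 hold for platelets leads to a restart one level lower; for isolated neutropenia, G-CSF with the dose maintained is an alternative. Response is judged at 12 weeks, which is three 28-day cycles, so Day 1 of Cycles 2 and 3 falls inside the window that sets response status. The signature is tested against that status.

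**Working it through.** The plan states no figure to reproduce. The check sets the two rules side by side. Let B be the baseline count and c the Day 1 count.

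**Platelets.** Start (6.5.2): c ≥ 30,000 or c ≥ 0.5B, that is, c ≥ min(30,000, 0.5B). Hold (Table 2): c < 50,000 if B ≥ 50,000; c < 0.5B if B < 50,000.

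| Baseline | Start permitted from | Hold below | Overlap |
|---|---|---|---|
| 40,000 | min(30,000, 20,000) = 20,000 | 20,000 | none |
| 50,000 | min(30,000, 25,000) = 25,000 | 50,000 | 25,000 to <50,000 |
| 60,000 | min(30,000, 30,000) = 30,000 | 50,000 | 30,000 to <50,000 |
| 120,000 | min(30,000, 60,000) = 30,000 | 50,000 | 30,000 to <50,000 |

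The lower edge is 25,000 only at a baseline of 50,000. It rises to 30,000 at 60,000 and stays there. Below a baseline of 50,000 both rules turn on half of baseline and agree.

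**ANC, baseline up to 1000.** Start: c ≥ min(250, 0.5B). Hold: c < 0.5B. An overlap needs 0.5B > 250, so B > 500.

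| Baseline | Start permitted from | Hold below | Overlap |
|---|---|---|---|
| 500 | 250 | 250 | none |
| 600 | 250 | 300 | 250 to <300 |
| 800 | 250 | 400 | 250 to <400 |
| 900 | 250 | 450 | 250 to <450 |
| 1000 | 250 | 500 | 250 to <500 |

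**ANC, baseline above 1000.** The hold depends on the grade 4 cut-off G, which the documents do not give, so G is an assumption here. If G = 300 the overlap is 250 to <300; if 400, 250 to <400; if 500, 250 to <500. There is none if G is 250 or lower.

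**Stricter reading of the start rule.** If both parts of each count condition were required, the platelet start would be c ≥ max(30,000, 0.5B). An overlap would remain for baselines from 50,000 to just under 100,000; at 80,000 it is 40,000 to <50,000. The ANC overlap would disappear.

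**Sequence across cycles.** Take baseline platelets of 120,000 and a mid-cycle count of 40,000. Table 2 holds the drug. If the count is still 40,000 at Day 21, dosing is omitted for the rest of the cycle. On the next Day 1, 40,000 ≥ 30,000, so Section 6.5.2 permits a start one dose level lower. Counts are weekly in Cycles 1 to 3, and an unchanged 40,000 a week later meets the hold criterion again.

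**Inside Section 6.5.2.** Table 2 labels platelets below 50,000 as grade 3 or higher when baseline is 50,000 or more. If the fourth condition (grade 2 or lower) covers drug-related cytopenias, it blocks a start at 35,000 that the platelet condition in the same list allows.

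**The case against.** The best defence is the headings. Section 6.5.2 is about starting a cycle and has its own Day 1 pathway; Section 6.5.3 is about events during one. On that reading Section 6.5.2 governs Day 1. This is a natural reading, but the protocol does not state it, and Day 1 is itself a dosing day in a Days 1-28 schedule. Nor does it remove the problem: a patient started at 35,000 meets the hold criterion at the next weekly count with no change in condition.

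A second defence is that Section 6.5.2 gives permission while Table 2 gives an order, so the order wins. Then the 30,000 line would never decide anything: from a baseline of 50,000 up, Table 2 would require 50,000, and below that baseline, half of baseline is already under 25,000. The text does not say that this is intended.

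A third is that a lower start threshold could be deliberate because the dose is reduced after an omitted remainder of a cycle. That is possible, but the Section 6.5.2 thresholds also apply to patients with no reduction, and the Table 2 platelet hold does not depend on dose level.

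A fourth is that the fourth condition blocks the platelet example. If so, the inconsistency moves inside Section 6.5.2.

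Three stronger inferences are not supported:

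- A reader might take the 80% needing a delay or reduction (Section 6.1.1.3) as showing how often these rules will be used. That figure covers toxicity of any kind in del(5q) patients, whom this trial excludes.
- A reader might infer that different sites will apply different rules on Day 1. The schedule footnotes require the Day 1 visits of Cycles 2, 3 and 4 at the one centre.
- A reader might infer that the conflict affects every patient, or reaches down to 25,000 platelets at every baseline. The tables above show otherwise.

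**Conclusion.** The inconsistency is real and limited. It affects baseline platelets of 50,000 or more, for Day 1 counts from the smaller of 30,000 and half of baseline up to just under 50,000. It also affects baseline ANC above 500 and up to 1000, for Day 1 counts from 250 to just under half of baseline. Both follow from the protocol alone, reading the two parts of each start condition as alternatives, as written. For baseline ANC above 1000 the overlap rests on an assumed grade 4 cut-off above 250. There is no overlap on counts alone for baseline platelets below 50,000 or baseline ANC of 500 or less.

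The scope of the fourth condition in Section 6.5.2 is a separate ambiguity that bears on the same counts.

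The documents do not give the proportion of patients who will have a Day 1 count in these ranges, so the effect on exposure or response cannot be sized. The point should be settled because it concerns a safety rule for an expected toxicity.

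**What to change.** Amend Sections 6.5, 6.5.2 and 6.5.3 so that:

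1. no single count can both permit a start and require a hold;
2. the text states which section governs Day 1, and how a patient started under it is handled if the next count is unchanged;
3. the fourth condition in Section 6.5.2 states whether it covers cytopenias;
4. the count meant by grade 4 neutropenia is stated, so that the rule for baseline ANC above 1000 can be checked against the 250 line.

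The choice of thresholds belongs to the clinical team; none is proposed here. The cost is a wording amendment and its ethics review, with no effect on sample size or data collection.
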